#### 10.3 At any point in the study, will you request, use, or access health information in any form, including verbal, hard copy and electronic?

Yes  No

#### 10.4 Review the definitions below and respond to the following two questions. If you are not sure of the answers, email [contact] for assistance. The *Military Health System (MHS)* is defined as all DoD health plans and DoD health care providers that are organized under the management authority of, or in the case of covered individual providers, assigned to or employed by, the Defense Health Agency (DHA), the Army, the Navy, or the Air Force. *MHS workforce members* are employees, volunteers, trainees, and other persons whose conduct, in the performance of work for the MHS, is under the direct control of the MHS, whether or not they are paid by the MHS. *MHS business associates* are persons or entities that provide a service to the MHS and require protected health information (PHI) to provide the service.

##### Are you an MHS workforce member?

Yes, I am an MHS workforce member  
 No, I am not an MHS workforce member

##### Are you an MHS business associate?

Yes, I am an MHS business associate

No, I am not an MHS business associate

#### 10.5 Have you consulted with an MHS data expert to determine the data elements required for your study?

Consulting with a data expert often saves time later in the compliance process because the data expert can advise on the data available in the numerous MHS information systems, the quality of that data and the methods for encrypting and collapsing data. To schedule a consult with an MHS data expert, send an email to: **([contact])**

Yes, then complete the questions below according to the data consult  
 No, then complete the questions below according to the best of your knowledge

#### 10.6 Indicate how you will request data from the MHS. Select all that apply.

Talking with MHS health care providers or MHS health plans about specific research participants  
 Obtaining MHS hard copy records specific to research participants  
 Obtaining data from an MHS information system(s)

#### 10.7 If you are obtaining data from an MHS information system(s), indicate whether you plan to receive a data extract or whether you plan to access an MHS information system directly to create a data set.

A data extract is when the MHS or a contractor provides the data set directly to the researcher. When receiving a data set through data extract, the researcher may indicate whether the data elements should be provided as is, encrypted or collapsed. In contrast to a data extract, access to an information system means that the researcher may directly access an MHS information system and create a data set for the research study

Data Extract  
 Access

#### 10.8 Do you intend to request de-identified data from the MHS in your research study?

There are different two methods for de-identifying data pursuant to HIPAA:

- 1) Safe Harbor Method: Removing all of the identifiers listed in Table 1 below, provided that the researcher does not have actual knowledge that the remaining data can be used alone or in combination with other information to identify the individual who is the subject of the information
- 2) Statistical Method: An expert, with appropriate knowledge of and experience with generally accepted statistical and scientific principles and methods for rendering information not individually identifiable, determines that the data is not individually identifiable

Yes  No

#### 10.9 Indicate the MHS information system(s) from which you will seek to obtain data

If you do not know which system(s) contains the data elements you need, refer to the Guide for DoD Researchers on Using MHS Data or request guidance from an MHS data expert at: **[contact]**.

Below is a list of commonly used MHS systems. If the system from which you seek to obtain data is not listed below, list the name of the system in the "Other MHS Systems" category below **PHI Systems:**

MHS Information System	Requesting Data
: AHLTA	:  Yes
: CHCS	:  No

**PII-Only Systems:**

MHS Information System	Requesting Data
No records have been added	

**De-Identified Data & Other Systems:**

Information System	Requesting Data
No records have been added	

**10.10 Do you intend to merge or otherwise associate the requested data with data from any sources outside of the MHS, including other DoD systems that are not part of the MHS?**

Yes, will merge data  
 No, will not merge data

**10.11 Indicate the data elements about research participants or relatives, employers, or household members of the research participants that you will request from MHS hard copies or from MHS information systems.**

If you will merge data, also indicate non-MHS data elements about research participants or relatives, employers, or household members of the research participants that you will have access to in any form or medium.

Data Element(s)	MHS	Non-MHS Systems	MHS Hard Copies
1. Names			
2. Postal address with only town, city, state and zip code			
3. Postal address with all geographic subdivisions smaller than a state, including street address, city, county, precinct, zip code and their equivalent geocodes, except for the initial three digits of a zip code if, according to the current publicly available data from the Bureau of Census: 1) the geographic unit formed by combining all zip codes with the same three initial digits contains more than 20,000 people; and 2) the initial three digits of a zip code for all such geographic			

units containing 20,000 or fewer people is changed to 000				
4. Dates including all elements (except year) directly related to an individual, including birth date, admission date, discharge date, and date of death				
5. Ages over 89 and all elements of dates (including year) indicative of such age, unless you will only request a single category of "age 90 or older"				
6. Telephone numbers				
7. Fax numbers				
8. Electronic mail addresses				
9. Social Security numbers (SSNs)				
10. Medical record numbers				
11. Health plan beneficiary numbers				
12. Account numbers				
13. Certificate /license numbers				
14. Vehicle identifiers and serial numbers, including license plate numbers				

15. Device identifiers and serial numbers				
16. Web Universal Resource Locators (URLs)				
17. Internet Protocol (IP) address numbers				
18. Biometric identifiers, including finger and voice prints				
19. Full-face photographic images and any comparable images				
20. Any other unique identifying number, characteristic, or code (Diagnosis, DEERS ID, EDI-PI, Rank)				

If you are obtaining SSNs, provide a justification as to why and explain why a substitute cannot be used

**10.12 Do you believe it is possible for the MHS data to become identifiable because of triangulation, a small cell size, or any unique data element(s)?**

Triangulation means using different data elements that are not themselves identifiable but that when combined can be used to identify an individual. For example, triangulation would use rank and race together to determine the identity of an individual with a particular health condition.

Small cell size means that there is only a small number of eligible individuals that satisfy the category description. Guidance for acceptable cell size is available from the Centers for Medicare and Medicaid Services. For example, the rank category of four star generals with a particular diagnosis may be less than 30, so the rank category may need to be expanded to include lower ranks.

A unique data element includes any unique features that are not explicitly enumerated in the categories of data in rows 1 – 20 of the table above (in Section 10.10), but that could be used to identify an individual. Unique data elements include characteristics that are not themselves identifying, such as the rank of general or admiral, or a race or gender, but within the context of other information could be identifiable.

- Yes, I believe there is a reasonable possibility the MHS data will become identifiable
- No, I believe there is no reasonable possibility the MHS data will become identifiable

**10.13 Have you completed and uploaded an appropriate HIPAA document ( i.e. HIPAA Authorization will be obtained or Waiver/alteration of HIPAA Authorization is being requested)?**

- Yes
- No
- N/A

#### **10.14 Managing Data (Data Management and/or Sharing Plan) and/or Human Biological Specimens for this Study:**

Include in this section the plan for acquiring data (both electronic and hard copy), access during the study, data/specimen storage and length of time stored, shipment/transmission, and the plan for storage and final disposition at the conclusion of the study. Describe any data agreements in place for accessing data within and/or outside of your institution (e.g., Data Sharing Agreement, Data Use Agreement, Business Agreements, etc.)

**Acquiring Data:** The majority of participant data will be accrued via self-report questionnaire. We plan to retrieve diagnostic codes from their PT SOAP notes on AHLTA, and we will extract and de-identify whole SOAP notes from a subgroup of randomly selected participants. We will also use CHCS and AHLTA to determine when a participant has or will receive their fourth PT session, but this is merely for scheduling follow-up, and will not be retained as data.

**Data Entry and Integrity:** For data entered by participants into the REDCap surveys, we presume that participants responded correctly. All data collection tools completed on paper will be scanned and initially entered into REDCap by the proctoring research team member, who will mark the instrument as "Unverified" in REDCap. The scanned forms will be transmitted to [name] via SAFE, who will use them to verify the entered data, correct any inconsistencies, and then mark the instrument as "Complete." Our Excel database has been designed to draw values directly from downloaded REDCap data reports, reducing the potential for human error. We have also employed Excel's conditional logic programming and formatting to alert us if a participant's records are incomplete or mismatched.

**Access to Data:** The PI and research contractors ([name] and [name]) will have access to all study data, electronic and hard copy. NYU collaborators ([name] and [name]) will not have access to the original data; de-identified data and de-identified SOAP notes (for training evaluation) will be securely transmitted to them using the SAFE computer app.

**Data Storage:** All physical data and consent forms will be maintained in locked cabinets within a locked office at NMCP; forms collected at branch clinics may be temporarily stored in a similar two-lock situation until they can be transferred to the NMCP office. All digital data will be originally generated or collected on GFE at NMCP and maintained on that network. De-identified digital data will be transmitted to the NYU collaborators.

**Shipment/Transmission:** Any physical data that needs to be transferred from branch clinics to the NMCP office will be transported by a member of the NMCP research personnel. Transmission of digital data to NYU collaborators will be through the SAFE program.

**Conclusion:** The investigators will end support of dissemination of research data at the end of the project's contract period. The investigators will maintain the de-identified data in a secure location for a period of six years after the end of the contract period. At the end of six years the de-identified subject questionnaire data will be destroyed. The PI will notify CDMRP, the NMCP regulatory facilities such as IRB of record of the fulfillment of the requirement to destroy the research data at the end of the four and a half year period.

**Data Agreements:** Once the protocol is approved, NYU will apply for a DHA Data Sharing Agreement, with NYU listed as the applicant/primary contractor and HJF staff listed as subcontractors.

#### **10.15 Managing Data (Data Management and/or Sharing Plan) and/or Human Biological Specimens for Future Research:**

If the study involves collecting, storing, or banking human specimens, data, or documents (either by the Investigator or through an established repository) for FUTURE research, address.

How the specimens/data will be used, where and how data/specimens will be stored (including shipping procedures, storage plan, etc.), whether and how consent will be obtained, procedures that will fulfill subjects' request as stated in the consent, whether subjects may withdraw their data/specimens from storage, whether and how subjects may be recontacted for future research and given the option to decline, whether there will be genetic testing on the specimens, who will have access to the data/specimens, and the linkage, the length of time that data/specimens will be stored and conditions under which data/specimens will be destroyed.

N/A

## 11.0 Statistical/Data Analysis Plan

### 11.1 Statistical Considerations:

List the statistical methods to be used to address the primary and secondary objectives, specific aims, and/or research hypotheses. Explain how missing data and outliers will be handled in the analysis. The analysis plan should be consistent with the study objectives. Include any sub-group analyses (e.g., gender or age group). Specify statistical methods and variables for each analysis. Describe how confounding variables will be controlled in the data analysis

The characteristics of subjects including demographics and questionnaire responses will be summarized using descriptive statistics (e.g. mean  $\pm$  standard deviation for continuous variables, and counts (%) for categorical variables). Alternatively, response frequencies for the questionnaires will be determined and displayed in tabular and graphic formats. After examining the response frequencies, some variable categories will be collapsed in order to allow further analysis using them as dependent measures in subsequent analysis (chi-square and logistic regression analyses). For the continuous outcomes (quantitative measurements such as Pain Disability Index scale, self-efficacy, positive outcome expectations, catastrophizing, fear avoidance beliefs and distress in Aims 2 and 3), we will conduct the Kolmogorov-Smirnov or the Shapiro-Wilk test to confirm the normality prior to performing statistical analyses. We will detect outliers via histograms, box-plots, normal plots and summary statistics. Where appropriate, we will conduct logarithmic transformation on variables.

All analyses will be conducted using the principle of "intent-to-treat" in which every participant is assumed to have received his/her assigned intervention, regardless of adherence.

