### 11.5 Please provide a justification for your sample size

In order to achieve a statistical power of greater than 80% at an effect size of 0.3, we require a minimum of 200 participants to complete all follow-up in each cohort of the study, as detailed in the power analysis in Section 11.6. In order to account for a roughly 30% rate of attrition, we are requesting a sample size of 300 participants per arm, for a total of 600. Based on previous longitudinal studies by team members [name], [name], and [name], we believe that this is a conservative estimate considering the duration of each participant's involvement.

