## 11.6 Data Analysis Plan: Complete description: Background, Objectives, Design, Step by Step how the project is going to be done, Data analysis plan:

In order to assess for significant differences between two cohorts of patients, bivariate comparisons will first be conducted using a Chi-squared (Fisher exact) test to compare proportions of categorical (dichotomous outcomes) and an unpaired t-test for mean changes of continuous outcomes (i.e. Pain Disability Index scale, self-efficacy, positive outcome expectation, catastrophizing, fear avoidance beliefs and distress).

Alternatively, Wilcoxon nonparametric counterpart will be used for continuous variables where there is deviation from normality. These univariate analyses will be followed by multivariable regression methods for an adjustment of all other potential confounding variables. We will also use longitudinal logistic models (i.e., mixed-effects regression models with a random subject effect and GEE with exchangeable and independent correlations) to analyze the changes of the outcome at baseline at all follow-up times (baseline, post-treatment, at 6 months, and 1 year). Psychological outcomes will be analyzed at baseline and at post-treatment (approximately 4 weeks of enrollment). The models will be specified with random intercepts and slopes such that a linear trajectory representing outcomes will be compared between two arms. For example, longitudinal changes in all available continuous psychological outcomes over time of follow-up will be displayed using locally weighted smoothing scatter (lowess) plots, identifying nonparametric mean trajectories over time. Mean trajectories then will be modeled with mixed-effects linear regression models, and if necessary using segment-linear models to approximate non-linear mean trajectories for ease of interpretation. Group (arm)-specific (as well as individual-level) intercepts and slopes over the period of follow-up will be included as random effects, while other covariates such as other clinical or demographic confounders will be modeled as fixed effects. An interaction term will be also assessed to test group differences in outcomes over time. Residual-based diagnostics will be used to evaluate validity of model assumptions. Two sided p-values <0.05 will be considered to be statistically significant. All statistical procedures will be performed using R statistical package ([www.R-project.org](http://www.R-project.org)).

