**Table 2. Sample size and power**

Cohort size N (Total sample)	Loss to follow-up or noncompliance	Unpaired t- test	Fisher exact test			
			Effect size 	Power (%)	Effect size 	Power (%)
117 (234)	40%				0.30 (p1=0.8, p2=0.50)	95.4
100 (200)	30%	0.5	83.6			
167 (334)	40%				0.25 (p1=0.8, p2=0.55)	95.8
143 (286)	30%	0.5	94			
250 (500)	40%				0.20 (p1=0.8, p2=0.6)	96
215 (430)	30%	0.4	93.2			
334 (668)	40%				0.15 (p1=0.8, p2=0.65)	96
286 (572)	30%	0.3	84.9			

1 standardized mean difference of 2 groups  
2 absolute proportion difference of 2 groups with proportions ( $p_1 = P(\text{above MID in pre-training cohort})$ ,  $p_2 = P(\text{above MID in post-training cohort})$ )

**Missing data:** We will make every effort to prevent and avoid missing data. Even with the most robust processes, however, some missing data is inevitable. We will assess the mechanism of missing data by comparing patients with and without missing values on baseline and other complete information, to detect any patterns in demographics or other characteristics associated with missing data. First, the various missingness assumptions (missing completely at random: MCAR, missing at random: MAR or missing not at random: MNAR) will be tested by comparing subjects with missing and non-missing data. In order to incorporate uncertainty in handling missing data, we will perform a multiple imputation, which begins with a prediction of the missing data using the existing data from other variables. The missing values will then be replaced with the predicted values, and a full data set called the imputed data set will be created. This process iterates the repeatability and makes multiple imputed data sets. Each multiple imputed data set produced will be then analyzed using the standard statistical analysis procedures for complete data, and give multiple analysis results. Subsequently, by combining these analysis results, a single overall analysis result will be produced.

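### Collapsing ordered questionnaire items for chi-square and logistic regression would give up about 14 to 20 points of power at 0.3 SD, and Table 2 gives no power for a cut outcome at that effect

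*Combined protocol and SAP*

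**What the plan says.** Section 11.1 plans that "some variable categories will be collapsed in order to allow further analysis using them as dependent measures in subsequent analysis (chi-square and logistic regression analyses"). It does not name the variables, the cut points or the number of levels to be kept. The same section declares a set of outcomes continuous: "For the continuous outcomes (quantitative measurements such as Pain Disability Index scale, self-efficacy, positive outcome expectations, catastrophizing, fear avoidance beliefs and distress". Section 11.6 compares these by unpaired t-test on mean changes, with Wilcoxon as the fallback, and then by mixed-effects linear models. Categorical outcomes get a "Chi-squared (Fisher exact) test to compare proportions of categorical (dichotomous outcomes"), and longitudinal logistic models are also mentioned.

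The tables in Section 10.2 are badly extracted. They still show quality of life and outcome satisfaction as single 5-point items labelled as dependent variables. Aim 3 names both quality of life and satisfaction. Neither is in the list of continuous outcomes in 11.1 or 11.6.

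Section 11.5 sizes the study for "statistical power of greater than 80% at an effect size of 0.3", and says "we require a minimum of 200 participants to complete all follow-up in each cohort". In Table 2, footnote 2 defines the binary effect as "absolute proportion difference of 2 groups with proportions" above an MID. The MID is not given, and no analysis passage says which score it would cut.

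**The concern.** Reducing an ordered outcome to two levels discards information. The loss occurs even when the cut is fixed in advance and chosen blind to cohort, so it is separate from the question of choosing cuts after seeing the data. Collapsing is also not needed to make analysis possible. A proportional-odds model or a Wilcoxon test uses every level, and the plan already treats outcome expectations, described in Section 10.2 as a 5-point single item, as continuous.

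At stake is how a null result is read. If the true effect is the 0.3 SD the study is sized for, a non-significant chi-square on quality of life or satisfaction could be taken as no effect of the training, when the uncollapsed data would have had roughly the promised power. Table 2 does not warn of this. Its bolded rows put 96% for a binary outcome next to 84.9% for a continuous one.

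**Working it through.** **Inputs from the documents.** Two-sided alpha 0.05 and 1:1 allocation (11.6); effect 0.3 SD and 200 completers per arm (11.5); 300 enrolled per arm with about 30% attrition, so 300 × 0.7 = 210.

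**Assumptions.** Normal or latent-normal outcomes, equal SD and a pure shift. The documents give neither the MID nor any response distribution, so ranges are shown.

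**1. Reproduce the plan's figure.** Table 2's 0.3 row has 286 × 0.7 ≈ 200 per arm. The noncentrality is 0.3 × √(200/2) = 3.00 on 398 degrees of freedom, which gives power 84.9%, as stated. At 210 per arm it is 86.6%.

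**2. The same 0.3 SD shift cut in two.** If a proportion p of the control cohort lies above the cut, the other cohort has Φ(Φ⁻¹(p) + 0.3). Power by exact enumeration at 200 per arm:

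| Control | Other cohort | Fisher | Chi-square |
|---|---|---|---|
| 44.0% (best case, midway) | 56.0% | 63.3% | 67.0% |
| 50% | 61.8% | 62.4% | 66.1% |
| 65% | 75.3% | 58.1% | 62.1% |
| 70% | 79.5% | 54.9% | 59.3% |

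At 210 per arm the highest values among the cuts tried are about 65.5% (Fisher) and 69% (chi-square). With the best cut, 80% power needs about 275 completers per arm (pooled normal approximation), against the 210 expected.

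**3. Five-level items.** Latent-normal shift of 0.3 SD and four assumed control distributions. The Wilcoxon test is tie-corrected, with 10,000 simulations.

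| Control distribution | Wilcoxon, 5 levels | Best two-level cut, Fisher | Best two-level cut, chi-square |
|---|---|---|---|
| .10, .20, .40, .20, .10 | 80.8% | 60.8% | 64.6% |
| .20 in each level | 80.4% | 62.8% | 66.6% |
| .05, .15, .30, .35, .15 | 80.2% | 62.4% | 66.1% |
| .30, .30, .20, .15, .05 | 80.5% | 62.8% | 66.6% |

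The smallest loss is 80.4 − 66.6 = 13.8 points (chi-square) and the largest is 80.8 − 60.8 = 20.0 points (Fisher). Off-centre cuts do worse: the worst Fisher values are 29.5%, 45.6%, 16.4% and 27.2% for the four distributions in order. Collapsing to three levels and using Wilcoxon keeps 75-77% at the best cuts, a loss of about 4 to 5 points.

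**4. What Table 2's bolded binary row assumes.** On a normal scale, 0.80 against 0.65 corresponds to Φ⁻¹(0.80) − Φ⁻¹(0.65) = 0.842 − 0.385 ≈ 0.46 SD. At 0.46 SD and 200 per arm the t-test has 99.5% power. The continuous and binary rows are therefore not comparable, and no row gives power for a cut outcome at 0.3 SD.

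**5. The 96% in that row.** 334 × 0.6 ≈ 200 per arm. For 0.80 against 0.65, Fisher gives 90.7% and the pooled-normal chi-square 92.2%. A one-sided normal test gives 95.9%, but the plan states two-sided tests. The other three binary rows reproduce.

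**The case against.** The strongest reply has four parts.

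- **Scale scores.** A reader might infer that the Pain Disability Index and similar scores will be cut at an MID in place of a full-scale analysis, and so lose the 84.9%. The documents do not support that. Sections 11.1 and 11.6 test these scores on the full scale, and the MID appears only in the power material. This objection stands. The above-MID comparison adds to the full-scale test and does not replace it. What remains open is that no primary analysis is named, so nothing says which result decides.
- **Which items are collapsed.** A reader might also infer that quality of life and satisfaction will certainly be collapsed. Section 11.1 names no items, and its treatment of outcome expectations points the other way. Duty status, which is not clearly ordinal, is a more natural candidate. The phrase logistic regression does not exclude an ordinal model either. This stands as a limit: the loss is conditional on how the rule is applied. The silence still needs filling, because the two items are left out of the continuous list and 11.6 speaks of categorical outcomes as dichotomous.
- **Size of the loss.** Treating 63% as the ceiling would be wrong for the tests named in 11.1. It is the Fisher value at exactly 200 per arm. Chi-square reaches about 67%, and about 69% at 210. Three levels would lose less than two.
- **Table 2.** It labels its two effect scales separately and claims no equivalence between them, so it should not be read as concealing anything. The point is only that it omits the case the study is sized for.

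**Conclusion.** The concern holds in a limited form. If the collapsing rule is applied to ordered 5-point outcomes and takes them to two levels, it costs about 14 to 20 points of power at 0.3 SD with 200 completers per arm: from about 80-81% to 61-63% (Fisher) or 65-67% (chi-square) at the best cut, and less power than that at off-centre cuts. This rests on a latent-normal shift and assumed response distributions.

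For the scale scores, an above-MID comparison at 0.3 SD has about 55-63% power (Fisher) or 59-67% (chi-square) for control rates of 44-70%, beside a planned full-scale test at 84.9%. It is a weaker supplementary test.

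Separately from these assumptions, the 96% in Table 2 does not reproduce at the stated sample size and two-sided level; it should be about 91% (Fisher) or 92% (chi-square).

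**What to change.** - **Section 11.1:** replace the collapsing sentence with a statement that ordered questionnaire items, including quality of life and outcome satisfaction, will be analysed on all response levels, by a proportional-odds model (mixed-effects or GEE for repeated measures) or a Wilcoxon test. Limit collapsing to display, to merging sparse adjacent levels, and to non-ordinal items such as duty status.
- **Section 11.6:** state that inference on PDI, PSEQ, PCS, FABQ and HADS rests on the continuous score, and that the proportion above the MID is supportive and reported with a confidence interval.
- **Table 2:** correct the 96%. Note that the continuous and binary rows assume different effects. Give responder power at 0.3 SD with the test, control rate and normality assumption named.

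The cost is wording and a table note, with no new data or participants; ordinal mixed and GEE models can be fitted in R, the package the plan names. The downsides are small. An odds ratio is less direct to explain than a percentage, and proportionality must be checked. The percentages can still be reported.
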